Title	Sequencing of Stereotactic Ablative Body Radiotherapy in combination with PD-1 blockade using Pembrolizumab in Metastatic Non-Small Cell Lung Carcinoma
Short title	Sequencing of SABR and Pembrolizumab in Lung Cancer (SABRSeq)
Sponsor	Peter MacCallum Cancer Centre
Study design	Phase Ib, two arm randomised study
Study objectives	
Primary Objective: To assess common toxicities associated with pembrolizumab when given before or after SABR in patients with metastatic NSCLC.
 
Secondary Objectives:
 
 • To describe response rate in: a) lesions treated with SABR, b) non-irradiated lesions and c) overall response. • To describe the event history (local progression, distant progression and death) of NSCLC patients treated with SABR in combination with pembrolizumab. • To estimate progression free survival and overall survival of NSCLC patients treated with SABR in combination with pembrolizumab. 
Exploratory Objectives:
 
 • Evaluate PD-L1 expression in baseline tissue. • Evaluate baseline and longitudinal cellular and molecular changes in archival tumour tissue, and/or fresh tumour biopsies. This will include, but not limited to tumour infiltrating lymphocytes (TILs), CD73 and other markers. • Evaluate baseline and longitudinal changes in immunological cellular subsets and cytokines within peripheral blood.
Number of sites	2 sites, one in Australia and one in Canada
Expected sample size	32 patients
Recruiting period	24 months

2. Trial Schema

3. Schedule of Events

Table 1: ARM 1 Schedule of events

Trial Phase:	Screening Phase	Treatment Phase			Follow-up Phase		Progression
Trial phase and windows	Screening -28 to -1	SABR Within 4 weeks of randomisation	Day 1 Cycle 1 7 days \pm 2 days from SABR	Day 1 Cycle 2-34 3 days \pm 2 days prior to each dose of pembrolizumab	Safety Follow-up 30 days \pm 3 days from date of last dose of pembrolizumab	Follow-up 3 months \pm 7 days from the last cycle of pembrolizumab	Upon first progression ¹
Clinical/Administrative Assessments							
Informed Consent	X						
Inclusion/Exclusion Criteria	X						
Demographics and Medical History	X						
Disease Specific Medical History including prior therapies	X						
SINS score for Spinal Targets	X						
Full Physical Examination	X		X	X			
Vital Signs and body measurements ²	X		X	X		X	
ECOG Performance Status	X		X	X		X	
Pregnancy Test (β -HCG) ³	X		X	X			
Review Adverse Events ⁴	X	X	X	X	X	X	
SABR		X					
Pembrolizumab			X	X			
Review Prior/Concomitant Medications	X	X	X	X	X		
New Anti-Cancer Therapy Status					X	X	X
Survival status						X	

Trial Phase:	Screening Phase	Treatment Phase			Follow-up Phase		Progression
Trial phase and windows	Screening -28 to -1	SABR Within 4 weeks of randomisation	Day 1 Cycle 1 7 days \pm 2 days from SABR	Day 1 Cycle 2-34 3 days \pm 2 days prior to each dose of pembrolizumab	Safety Follow-up 30 days \pm 3 days from date of last dose of pembrolizumab	Follow-up 3 months \pm 7 days from the last cycle of pembrolizumab	Upon first progression ¹
Laboratory Procedures/Assessments: analysis performed by LOCAL laboratory							
Haematology ⁵	X		X	X			As clinically indicated
Biochemistry ⁶	X		X	X			
Thyroid Function tests ⁷	X		X	X			
Coagulation profile ⁸	X		X	X			
Virology ⁹	X						
Tumour Evaluation							
CT scan (Brain, Chest, Abdo, Pelvis) reported with RECIST 1.1 or MRI ¹⁰	X			X		X	
Whole body bone scan ¹⁰ (if clinically indicated)	X			X		X	
Response assessment ¹⁰				X		X	
FDG-PET ¹⁰	X			X ¹¹			
Translational studies							
Metastatic tumour biopsy sample ¹²	X					X	X
Primary tumour biopsy sample ¹³	X						
Blood Collection ¹⁴ (serum and ctDNA)		X	X	X		X	X

Table 2: ARM 2 Schedule of events

Trial Phase:	Screening Phase	Treatment Phase			Follow-up Phase		Progression
Trial phase and windows	Screening -28 to -1	Day 1 Cycle 1 3 days \pm 2 days prior to the first dose of pembrolizumab	SABR 7 days \pm 2 days from cycle 1 day 1	Day 1 Cycle 2-34 3 days \pm 2 days prior to each dose of pembrolizumab	Safety Follow-up 30 days \pm 3 days from date of last dose of pembrolizumab	Follow-up 3 months \pm 7 days from the last cycle of pembrolizumab	Upon first progression ¹
Clinical/Administrative Assessments							
Informed Consent	X						
Inclusion/Exclusion Criteria	X						
Demographics and Medical History	X						
Disease Specific Medical History including prior therapies	X						
SINS score for Spinal Targets	X						
Full Physical Examination	X	X		X			
Vital Signs and body measurements ²	X	X		X		X	
ECOG Performance Status	X	X		X		X	
Pregnancy Test (β -HCG) ³	X	X		X			
Review Adverse Events ⁴	X	X	X	X	X	X	
SABR			X				
Pembrolizumab		X		X			
Review Prior/Concomitant Medications	X	X	X	X	X		
New Anti-Cancer Therapy Status					X	X	X
Survival status							X
Laboratory Procedures/Assessments: analysis performed by LOCAL laboratory							
Haematology ⁵	X	X		X		As clinically	

Trial Phase:	Screening Phase	Treatment Phase			Follow-up Phase		Progression
Trial phase and windows	Screening -28 to -1	Day 1 Cycle 1 3 days \pm 2 days prior to the first dose of pembrolizumab	SABR 7 days \pm 2 days from cycle 1 day 1	Day 1 Cycle 2-34 3 days \pm 2 days prior to each dose of pembrolizumab	Safety Follow-up 30 days \pm 3 days from date of last dose of pembrolizumab	Follow-up 3 months \pm 7 days from the last cycle of pembrolizumab	Upon first progression ¹
Biochemistry ⁶	X	X		X		indicated	
Thyroid Function tests ⁷	X	X		X			
Coagulation profile ⁸	X	X		X			
Virology ⁹	X						
Tumour Evaluation							
CT scan (Brain, Chest, Abdo, Pelvis) reported with RECIST 1.1 or MRI ¹⁰	X			X		X	
Whole body bone scan ¹⁰ (if clinically indicated)	X			X		X	
Response assessment ¹⁰				X		X	
FDG-PET ¹⁰	X			X ¹¹			
Translational studies							
Fresh tumour biopsy sample ¹²	X					X	X
Archival tumour biopsy sample ¹³	X						
Blood Collection ¹⁴ (serum and ctDNA)		X	X	X		X	X

Table 1 and 2 Footnotes

1. Beyond first progression, every effort should be made to record results of subsequent tumour assessments. In addition, details of any new anti-cancer treatment commenced is to be collected.
2. Vital signs include blood pressure, heart rate, respiratory rate and temperature. Body measurements including height and weight (height only required at screening).
3. Urine or serum pregnancy test for patient of childbearing potential should be performed within 7 days randomisation and also 72 hours before first dose of pembrolizumab. If the urine test is positive or cannot be confirmed as negative, a serum pregnancy test will be required.
4. Baseline abnormalities must be recorded from signature of informed consent to prior to start of treatment. Adverse events (using CTCAE v4.03) are then required to be reported on completion of SABR, day 1 of every pembrolizumab cycle and at every follow-up visit. If at any time, a patient commences a new anti-cancer therapy, recording of adverse events is no longer required.

Laboratory Procedures/Assessments – All diagnostic laboratory tests should be performed within 10 days of randomisation (to determine eligibility), and also on day 1 ± 3 days of every cycle of pembrolizumab (unless otherwise specified)

5. Haematology: Haematocrit, haemoglobin, platelet count, white blood cell count (total and differential), red blood cell count, absolute neutrophil count and absolute lymphocyte count.
6. Biochemistry: calcium chloride, glucose, phosphorus, potassium, sodium, magnesium, total protein, Liver Function Tests: Albumin, Alkaline Phosphatase (ALP), Alanine Aminotransferase (ALT), Aspartate Aminotransferase (AST), Lactate Dehydrogenase (LDH), Gamma-Glutamyl Transferase (GGT), total bilirubin (+direct bilirubin if total bilirubin is elevated above the ULN), Kidney Function Tests: Urea, creatinine.
7. Thyroid Function tests: T3, T4 and TSH. To be performed at during screening, day 1 cycle and every 6 weeks thereafter.
8. Coagulation Profile: PT (INR), aPTT.
9. Virology: HIV, Hepatitis B and C tests only required for those patients at risk of prior or current active infection as determined by the investigator. To be performed within 21 days of randomisation.

Tumour evaluation

10. Radiological tumour assessments will be performed by CT scan (or MRI as required if tumour is in extremity) at screening (within 6 weeks of randomisation), prior to cycle 3, 5, 7 and every 3 cycles thereafter in the treatment phase. Then 3 monthly in the follow-up phase until the last patient recruited completes 24 months of follow-up, unless evidence of progression earlier. Whole body bone scan (WBBS) will be performed if clinically indicated at the same time points. Formal response assessment (using RECIST 1.1, irRECIST, Peter Mac Metabolic Response Criteria and PERCIST 1.0.) at each scheduled scan time point. Response should be confirmed with repeat imaging 4 to 8 weeks later by the same imaging modality. CT of brain only required at screening.
11. FDG PET at baseline and prior to cycle 5 of pembrolizumab. (note: a contemporaneous CT brain/chest/abdo pelvis performed at the same time will fulfill the CT requirement 3 month follow-up)

Biological Evaluations

12. A fresh biopsy of the primary or metastatic lesion will be performed at screening (within 12 weeks of randomisation). and 3 months post completion of SABR. This will ideally be the same site as biopsied before at screening. In event of disease progression, a sample from progressing metastatic site(s), if feasible, is requested. Refer to the SABRseq laboratory manual for further details on handling and shipping of tumour samples.
13. If a fresh biopsy of the primary or a metastatic lesion cannot be provided (e.g. inaccessible or patient safety concern) an archived specimen can be submitted only upon agreement from the study principal investigators. Refer to the SABRseq laboratory manual for further details on handling and shipping of tumour samples.
14. To be collected at screening, prior to SABR, prior to each pembrolizumab dose and 3 monthly during follow-up. Refer to the SABRseq laboratory manual for further details on blood sample collection, handling and shipping.

4. Background

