11. Has had a prior anti-cancer monoclonal antibody (mAb) within 4 weeks prior to randomisation or who has not recovered (i.e., \leq Grade 1 or at baseline) from adverse events due to agents administered more than 4 weeks earlier.
12. Has diagnosed and/or treated additional malignancy within 5 years prior to randomisation with the exception of: curatively treated basal cell carcinoma of the skin, squamous cell carcinoma of the skin, curatively treated early stage cervical

cancer, breast cancer or prostate cancer with no evidence of active disease. Other exceptions may be considered following consultation with the principal investigator

13. Has active autoimmune disease that has required systemic treatment in the past 2 years (i.e. with use of disease modifying agents, corticosteroids or immunosuppressive drugs). Replacement therapy (e.g. thyroxine, insulin, or physiologic corticosteroid replacement therapy for adrenal or pituitary insufficiency, etc.) is not considered a form of systemic treatment.
14. Has a history of (non-infectious) pneumonitis that required steroids or current pneumonitis.
15. Has had any systemic anti-cancer therapy or radiation therapy within 4 weeks prior to randomisation
16. Has known interstitial lung disease
17. Has an active infection requiring systemic therapy.
18. Has a history or current evidence of any condition, therapy, or laboratory abnormality that might confound the results of the trial, interfere with the patient's participation for the full duration of the trial, or is not in the best interest of the patient to participate, in the opinion of the treating investigator.
19. Has known psychiatric or substance abuse disorders that would interfere with cooperation with the requirements of the trial.
20. Has received prior therapy with an anti-PD-1, anti-PD-L1, or anti-PD-L2 agent.
21. Has a known history of Human Immunodeficiency Virus (HIV) (HIV 1/2 antibodies).
22. Has known active Hepatitis B (e.g., HBsAg reactive) or Hepatitis C (e.g., HCV RNA [qualitative] is detected).
23. Has received a live vaccine within 30 days of randomisation.

Note: Seasonal influenza vaccines for injection are generally inactivated flu vaccines and are allowed; however intranasal influenza vaccines (e.g., Flu-Mist®) are live attenuated vaccines, and are not allowed.

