8.6 Survival Follow-up

Patients who discontinue trial treatment due to progression, progress during follow-up or commence a new systemic treatment will be followed for survival only. Survival status will be assessed every 3 months until death, withdrawal of consent, or the end of the study, whichever occurs first. Where possible, every effort should be made to record results of subsequent tumour assessments and any new anti-cancer therapies.

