8.13 Non-Permitted Medications

Patients are prohibited from receiving the following therapies during the screening and treatment phase of this trial:

- Antineoplastic systemic chemotherapy or biological therapy
- Immunotherapy not specified in this protocol
- Chemotherapy not specified in this protocol
- Investigational agents other than pembrolizumab
- Radiation therapy

Note: Radiation therapy to a symptomatic lesion(s) or to the brain may be allowed at the investigator's discretion.

- Live vaccines within 30 days prior to randomisation and while participating in the trial. Examples of live vaccines include, but are not limited to, the following: measles, mumps, rubella, varicella/zoster, yellow fever, rabies, BCG, and typhoid vaccine.
- Systemic glucocorticoids for a chronic inflammatory disorder. The use of physiologic doses of corticosteroids on a regular repetitive basis for a medical condition may be approved after consultation with the Principal Investigator.

Patients who, in the assessment by the investigator, require the use of any of the aforementioned treatments for clinical management should be removed from the trial. Patients may receive other medications that the investigator deems to be medically necessary.

The exclusion criteria describe other medications that are prohibited in this trial.

There are no prohibited therapies during the follow-up phase.

9. Trial Radiotherapy Treatment

The treatment regimen involves the delivery of a single fraction of highly conformal SABR to 1 to 3 metastases; delivered with either photons, electrons or mixed modalities. The maximal number of metastases within this range should be irradiated, however, at least one metastases defined as measurable disease must not be irradiated. The first dose of pembrolizumab will be delivered either 7 days (+/- 2 days after (ARM 1) or 7 days (+/- 2 days) before (ARM 2) the SABR treatment and will be continued for up to 24 months (34 cycles).

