10.2 Continuing Pembrolizumab

In the event of radiological progression, pembrolizumab may be continued if there is evidence of clinical benefit in the opinion of the investigator if there are no signs or

symptoms indicating unequivocal disease progression, no decline in ECOG performance status attributed to disease progression and no growth of the tumour in critical sites. If radiological progression is still documented pembrolizumab may still be continued until there is unequivocal symptomatic deterioration attributed to disease progression that requires initiation of new systemic therapy. Radiotherapy to progressing or symptomatic sites as per standard clinical practice is allowed.

11. Labeling, Packaging, Storage and Return of Clinical Supplies

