12.6 Adverse Events Reporting

All adverse events, which occur whilst the patient is enrolled on the trial, must be reported in the patients' medical records and recorded on the relevant CRF.

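### Footnote 4 lets adverse-event recording stop at an undefined new anti-cancer therapy, even while pembrolizumab is still being given, and conflicts with section 12.6

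*Combined protocol and SAP*

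**What the plan says.** **The stop rule.** Footnote 4 (section 3, Table 1 and 2 Footnotes) requires adverse events on completion of SABR, then at "day 1 of every pembrolizumab cycle and at every follow-up visit". It then adds: "If at any time, a patient commences a new anti-cancer therapy, recording of adverse events is no longer required".

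**Radiotherapy during pembrolizumab.** Section 8.13 prohibits radiation in the screening and treatment phases, with an exception: "Radiation therapy to a symptomatic lesion(s) or to the brain may be allowed at the investigator's discretion". Section 10.2 says that after radiological progression "pembrolizumab may be continued if there is evidence of clinical benefit in the opinion of the investigator", subject to conditions, and closes with: "Radiotherapy to progressing or symptomatic sites as per standard clinical practice is allowed".

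**The competing rule.** Section 12.6 has no exception for new therapy: "All adverse events, which occur whilst the patient is enrolled on the trial, must be reported" in the medical records and recorded on the CRF. Sections 8.2.3 and 8.3.3 list adverse-event assessment for cycles 2 to 34.

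**What depends on it.** The primary endpoint (5.3) is treatment-related adverse events of any grade, early and late. Section 14.5 tabulates the maximum grade per patient among all who received at least one SABR treatment and one pembrolizumab dose.

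**The concern.** The stop rule has two gaps. Its trigger is undefined, and it can act before trial drug has ended. Elsewhere the protocol can be more exact. Section 8.6 says that patients who "commence a new systemic treatment will be followed for survival only". Exclusion 15 names systemic therapy and radiation separately: "Has had any systemic anti-cancer therapy or radiation therapy within 4 weeks prior to randomisation". Section 12.9 ties a new anticancer therapy to a window after treatment has ceased. Footnote 4 does none of this.

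Take a patient with a painful bone lesion who is irradiated around cycle 6 and continues pembrolizumab to cycle 12. A site that treats the radiotherapy as new anti-cancer therapy could stop recording at cycle 6. A non-serious related event at cycle 9 might then be missing from the 14.5 tables, while the patient still counts in the denominator and contributes only the grades seen earlier. This patient has had pembrolizumab plus further radiotherapy, so the events bear on the trial's question about combined toxicity.

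The trial has two sites. If one follows the footnote and the other follows 12.6, their primary-endpoint data are not comparable. The point concerns recording during trial treatment, not late toxicity after treatment has been stopped for progression.

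**Working it through.** **1. Which rule applies to which event while pembrolizumab is being given, after permitted radiotherapy?**

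| Source | Events covered | Ends at a new therapy? |
|---|---|---|
| Footnote 4 | all adverse events | yes, at any time; trigger undefined |
| 12.6 | all adverse events while enrolled | no |
| 8.2.3, 8.3.3 | adverse-event assessment, cycles 2–34 | not stated |
| 12.8.1 | serious events, to 30 days after final protocol treatment | no |
| 12.9 | overdose without effects; one liver-test pattern | only after treatment has ceased |

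Serious events and the two events of clinical interest are protected whichever way the footnote is read. The exposed group is non-serious events outside 12.9. For these, footnote 4 and 12.6 give opposite answers, and nothing ranks one above the other. The footnote's own day-1 rule does not settle it, because the stop sentence follows that rule and qualifies it.

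**2. How much slack does the sample size have?**

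Inputs (14.9 and Table 9): 16 patients per arm, 32 overall, true toxicity rate 10%, target 80% per arm. The formula is P(at least one) = 1 − (1 − p)^n.

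- Per arm: 1 − 0.9^16 = 0.815, as in Table 9.
- Overall: 1 − 0.9^32 = 0.966, as in Table 9.
- With 15 fully observed patients: 1 − 0.9^15 = 0.794, below 80%.

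The other Table 9 rows also reproduce. Sixteen is the smallest n that reaches 80% at a 10% rate.

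**3. Illustration only.**

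The documents give no rate of on-treatment radiotherapy. Assume that k patients per arm have recording stopped early, and that a share f of their toxicity risk falls after the stop. Then P = 1 − 0.9^(16−k) × [1 − 0.1(1 − f)]^k. For example, k = 2 and f = 0.5 gives 1 − 0.9^14 × 0.95^2 = 0.794.

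| k per arm | f = 0.25 | f = 0.5 | f = 1 |
|---|---|---|---|
| 0 | 0.815 | 0.815 | 0.815 |
| 1 | 0.810 | 0.804 | 0.794 |
| 2 | 0.804 | 0.794 | 0.771 |
| 4 | 0.793 | 0.770 | 0.718 |

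Overall (n = 32, k stopped in each arm), f = 0.5 gives 0.962, 0.957 and 0.947 for k = 1, 2 and 4. The model treats every event after the stop as lost, serious ones included, so it overstates the loss. Both k and f are assumed.

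**The case against.** The strongest reply is that the trigger is inferred. No passage says that permitted radiotherapy is a new anti-cancer therapy. The protocol's vocabulary is loose: 8.4 uses two different terms for new treatment in the same paragraph. The context also leans towards a systemic or post-treatment meaning. Section 10.2 names new systemic therapy as the point at which pembrolizumab ends and deals with radiotherapy separately. Sections 12.9 and 12.11 place new anticancer therapy after cessation of treatment or completion of the trial. The schedules do not collect new-therapy status at any treatment-cycle visit. In addition, recording that is no longer required is not forbidden, and a site that follows 12.6 loses nothing.

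Most of this stands. It shows that the sponsor may well have intended the narrower meaning, but it does not put that meaning into the text. The new-therapy status row is also marked at first progression, and 10.2 allows pembrolizumab to continue after radiological progression, so the row does not confine the term to the period after treatment.

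A reader might also infer that the 14.10 safety trigger would miss grade 3–4 pneumonitis or colitis. The documents give that little support. Table 4 calls for immediate intravenous steroids for grade 3–4 pneumonitis, and 12.3 says that events which may need intervention to prevent a serious outcome should usually be classed as serious. Such events would normally reach the sponsor under 12.8.1. Nothing in 14.10 limits its count to events recorded under footnote 4.

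**Conclusion.** The point holds as a conflict over data collection: an undefined trigger, no link to the end of pembrolizumab, and a contradiction with 12.6 that no passage resolves. What is exposed is non-serious adverse events on treatment in patients given permitted radiotherapy, and only where a site counts that radiotherapy as new therapy and follows the footnote rather than 12.6.

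A reader might go further and conclude that on-treatment toxicity will go unrecorded, or that the design misses its 80% target. The documents do not support either conclusion. The first needs a definition that they never give. The second needs a radiotherapy rate and a timing of risk that they do not contain; with one patient per arm affected and half the risk after the stop, the figure is still 0.804. What can be said without assumption is that the per-arm criterion has almost no slack (0.815 with 16 patients, 0.794 with 15), so even a small avoidable loss matters. The clarification should be made, because it protects the primary endpoint at very low cost.

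**What to change.** Keep the footnote 4 schedule as it is (SABR, day 1 of every cycle, every follow-up visit) and replace only its last sentence with:

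*Recording may end early only when a new systemic anti-cancer therapy starts after trial pembrolizumab has been permanently stopped; radiotherapy permitted under 8.13/10.2 does not end recording.*

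Align 8.4 and 12.6 with this, so that one rule governs. Record the date and site of any such radiotherapy, so that later events can be identified in the 14.5 output.

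The new sentence should not make recording end at the safety follow-up visit, about 30 days after the last dose. That would remove the 3-monthly collection in footnote 4 and 8.5, although the endpoint includes long-term toxicity.

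**Cost.** One sentence, two aligned sections and CRF guidance. Patients are already seen at every cycle, so no visits are added. Some recorded events will be due to the palliative radiotherapy; the 12.4 attribution codes and the radiotherapy date can separate these. The change concerns data collection only and takes no view on whether such radiotherapy or continued pembrolizumab should be given.

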8.2.3 Cycle 2 to Cycle 34 Assessments

The following assessments will be performed within 3 days prior to pembrolizumab dosing in each cycle, unless otherwise specified.

- Physical examination
- Vital signs and weight
- Documentation of concomitant medications
- Documentation of ECOG performance status
- Laboratory studies including FBE, biochemistry and coagulation, hepatic and kidney
- Thyroid function tests (every 6 weeks)
- Radiological evaluation with a CT Chest/Abdomen and Pelvis or MRI (prior to cycle 3, 5, 7 and every 3 cycles thereafter)
- FDG-PET scan prior to cycle 5
- Whole body bone scan (prior to cycle 3, 5, 7 and every 3 cycles thereafter, only if clinical indicated)
- Response assessment (prior to cycle 3, 5, 7 and every 3 cycles thereafter)
- Adverse events assessment
- Pregnancy test in female patients with child bearing potential.
- Blood samples for correlative studies

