9.3 Treatment Schedule

Study therapy should commence within 28 days of patient randomisation on the study. A single dose of 20 Gy should be prescribed, although a single 18Gy fraction can be used as an alternative for a centrally located lung lesion or a spinal lesion with a SINS score of ≥ 7 after review at SABR chart round. Ideally all treatments should be performed on the same day. One or more lesions must be deemed suitable for treatment with SABR; up to 3 lesions may be treated. The choice of treatment sites for SABR is at clinician discretion, but should encompass different types of metastatic sites where possible (e.g. bone and/or lymph node and/or visceral organ). The maximal number of metastases within this range should be irradiated, however, at least one metastases defined as measurable disease must not be irradiated. The use of single 4mg dose of prophylactic dexamethasone prior to SABR treatment is permitted.

10. Trial Pembrolizumab Treatment

Pembrolizumab treatment should begin either 7 days (+/- 2 days) before the first SABR treatment or 7 days (+/- 2 days) after the last SABR treatment

Pembrolizumab 200 mg will be administered as a 30 minute IV infusion every 3 weeks for 34 cycles. Sites should make every effort to target infusion timing to be as close to 30 minutes as possible. However, given the variability of infusion pumps from site to site, a window of -5 minutes and +10 minutes is permitted (i.e., infusion time is 30 minutes: -5 min/+10 min).

Pembrolizumab treatment should be administered on Day 1 of each cycle after all procedures/assessments have been completed as detailed in Sections 8.2 and 8.3. Trial treatment may be administered up to 3 days before or after the scheduled Day 1 of each cycle due to administrative reasons.

All trial treatments will be administered on an outpatient basis.

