3.6 Confirmation

- The main goal of confirmation of objective response is to avoid overestimating the response rate observed. In cases where confirmation of response is not feasible, it should be made clear when reporting the outcome of such studies that the responses are not confirmed.
- To be assigned a status of PR or CR, changes in tumour measurements must be confirmed by repeat assessments that should be performed no less than 4 weeks after the criteria for response are first met. Longer intervals as determined by the study protocol may also be appropriate.
- In the case of SD, follow-up measurements must have met the SD criteria at least once after study entry at a minimum interval (in general, not less than 6-8 weeks) that is defined in the study protocol.

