2.3. Follow-up: New Non-Measurable Lesions Definition and Assessment

- All new lesions not selected as new measurable lesions are considered new non-measurable lesions and are followed qualitatively. Only a massive and unequivocal progression of new non-measurable lesions leads to an overall assessment of irPD for the timepoint. Persisting new non-measurable lesions prevent irCR.

2.4. irRC Overall Tumor Assessments

- **irCR**, complete disappearance of all measurable and non-measurable lesions. Lymph nodes must decrease to < 10 mm in short axis. Confirmation of response is not mandatory.
- **irPR**, decrease of $\geq 30\%$ in TMTB relative to baseline, non-target lesions are irNN, and no unequivocal progression of new non-measurable lesions.
- **irSD**, failure to meet criteria for irCR or irPR in the absence of irPD.
- **irNN**, no target disease was identified at baseline and at follow-up the patient fails to meet criteria for irCR or irPD.
- **irPD**, minimum 20% increase and minimum 5 mm absolute increase in TMTB compared to nadir, or irPD for non-target or new non-measurable lesions. Confirmation of progression is recommended minimum 4 weeks after the first irPD assessment.
- **irNE**, used in exceptional cases where insufficient data exists.
- **irND**, in adjuvant setting when no disease is detected.

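### Footnote 10's 4 to 8 week confirmation window does not fit its own scan schedule from cycle 7 on, and section 14.7 does not say whether responses must be confirmed

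*Combined protocol and SAP*

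**What the plan says.** **Schedule and window.** Footnote 10 to Tables 1 and 2 places CT or MRI "prior to cycle 3, 5, 7 and every 3 cycles thereafter in the treatment phase". It continues: "Then 3 monthly in the follow-up phase until the last patient recruited completes 24 months of follow-up". After calling for assessment by all four criteria sets, it adds: "Response should be confirmed with repeat imaging 4 to 8 weeks later by the same imaging modality". Section 10 fixes the cycle length: "Pembrolizumab 200 mg will be administered as a 30 minute IV infusion every 3 weeks for 34 cycles".

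**Appendices.** Appendix 3, section 3.6 (RECIST 1.1) makes CR or PR status depend on repeat assessments that "should be performed no less than 4 weeks after the criteria for response are first met". It sets no upper limit, leaves longer intervals to the protocol, and lets unconfirmed responses be reported if they are labelled as such. Appendix 4, section 2.4 (irRECIST) says under irCR: "Confirmation of response is not mandatory". Its irPR entry is silent.

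**Analysis.** Section 14.7 reports CR+PR at 6 and 12 months after the start of SABR with exact 95% intervals and compares overall response between arms with Fisher's exact test. It does not mention confirmation.

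**Visit lists.** Sections 8.2.3, 8.3.3 and 8.5 list routine scans and no confirmatory scan. Section 8.3.3 (Arm 2) makes CT and response assessment conditional on clinical indication; section 8.2.3 (Arm 1) does not. Footnote 11 schedules one PET after baseline, before cycle 5.

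**The concern.** The window and the schedule sit in one footnote and match only for responses first seen at cycle 3 or 5. After that, an in-window confirmation needs someone to order an extra scan. The trial is open label (section 7.5), so that person knows the arm, and the resulting rate is compared between arms. The appendices and section 14.7 do not settle what happens when the extra scan is not done. The analyst would then decide, with data in hand, whether such a patient is a responder. What is at stake is the reproducibility and between-arm fairness of the CR+PR rates.

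**Working it through.** **Inputs.** Cycle length 21 days and 34 cycles (section 10). Scans before C3, C5, C7, then C10, C13, ... C34 (footnote 10): 12 scans, 11 gaps. Confirmation window 28 to 56 days (footnote 10). Assessments fall 1 to 5 days before the dose (Tables 1 and 2); section 8.2.3 gives a narrower range: "The following assessments will be performed within 3 days prior to pembrolizumab dosing in each cycle, unless otherwise specified". Dosing, from section 10: "Trial treatment may be administered up to 3 days before or after the scheduled Day 1 of each cycle due to administrative reasons". Follow-up visits ±7 days (Tables 1 and 2).

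**Gaps.** Scan day = (cycle − 1) × 21. C3, C5, C7 and C10 fall on days 42, 84, 126 and 189. The 1-to-5-day scan window moves a gap by up to 4 days either way. The dosing window adds up to 3 + 3 = 6 days.

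| Gap | Nominal | Scan window only | Scan and dosing windows | Within 28–56 days? |
|---|---|---|---|---|
| C3–C5, C5–C7 (2 gaps) | 42 days | 38–46 | 32–52 | Yes |
| C7–C10 to C31–C34 (9 gaps) | 63 days | 59–67 | 53–73 | No, 7 days over |
| 3-monthly follow-up | about 91 days | 77–105 | not applicable | No |

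With section 8.2.3's window of 0 to 3 days, the 63-day gap ranges over 60–66 days, or 54–72 with dosing. Reaching 56 days needs 7 of the 9 or 10 days of available slack to fall in one direction.

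**One patient, two answers.** Take a PR first seen before C7 (day 126) and still present before C10 (day 189). The interval is 189 − 126 = 63 days. Appendix 3: 63 ≥ 28, confirmed. Footnote 10: 63 > 56, not confirmed.

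**Where the reporting times fall.** With SABR on one day, 7 days before C1 in Arm 1 and 7 days after it in Arm 2, the scan nearest 6 months is C10: (189 ± 7)/7 = 28 and 26 weeks after SABR. The scan nearest 12 months is C19 (day 378): (378 ± 7)/7 = 55 and 53 weeks. Both lie in the 9-weekly part.

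**Size.** The exact (Clopper-Pearson) interval reproduces Table 10: 8/16 = 50% (24.7–75.3; plan 25–75) and 6/16 = 37.5% (15.2–64.6; plan 15–65). One patient is 1/16 = 6.25 points. As an illustration, 8/16 falling to 7/16 gives 43.75% (19.8–70.1).

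**After the fix.** Under a rule of at least 28 days at the next scheduled CT/MRI, the shortest on-treatment gap with all windows stacked is 32 days and the shortest follow-up gap is 77. All 11 on-treatment gaps qualify, against 2 of 11 now.

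**The case against.** The strongest reply is that footnote 10 never ties confirmation to the next routine scan. It can be read as ordering a repeat scan whenever a response is seen, in both arms, and nothing forbids one. That stands: a reader might infer that the window cannot be met after cycle 7, and the text does not support that. What remains is that no visit list carries the scan, so doing it is left to the site.

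A reader might also infer three contradictory confirmation rules. Appendix 3's 4-week minimum is compatible with 4 to 8 weeks; it is looser, and the two part only when the repeat scan comes after 8 weeks. Appendix 4's waiver belongs to irCR alone and does not govern RECIST 1.1.

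A third inference is that late responses are lost or undercounted. No section says so. Section 14.7 refers to RECIST 1.1 definitions, and Appendix 3 makes CR or PR conditional on confirmation, which points that way. But Appendix 3 also allows labelled unconfirmed reporting where confirmation is not feasible. The defect is that 14.7 does not choose.

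Finally, keeping 4 to 8 weeks and listing the extra scan would also remove the mismatch: a scan two cycles (42 days) after first response falls inside the window. That is a legitimate alternative, at the price of added imaging.

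**Conclusion.** The mismatch holds on the document's own figures. For responses first seen at cycle 7 or later, the next scheduled CT/MRI comes at about 9 weeks on treatment or about 13 weeks in follow-up. It falls outside the window unless visit windows stack near their extremes. Section 14.7 does not say whether confirmation is required or how an unconfirmed response counts.

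Each reclassified patient shifts an arm's rate by 6.25 points if all 16 patients are in the denominator, and by more if the response-evaluable population is smaller. The number of such patients is unknown, because the documents give no time-to-response figures. It would be tempting to conclude that the 12-month rate suffers most, or that delayed responses are especially affected; nothing in the documents supports either ranking. The shift is also small beside the plan's own interval of 25–75% for 8/16.

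The calculation assumes undelayed 3-week cycles. Response is a secondary endpoint; the primary safety endpoint and the sample-size basis are untouched. The change should be made but is not critical.

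**What to change.** 1. In footnote 10, for RECIST 1.1 and irRECIST, replace the 4 to 8 week window with: *confirmed at the next scheduled CT/MRI, at least 4 weeks later*. Align Appendix 4 with this.
2. In section 14.7, state that this rule defines CR+PR at 6 and 12 months, and report the unconfirmed rates alongside.
3. State that PERCIST and Peter Mac metabolic responses are reported as unconfirmed. With one post-baseline PET, no same-modality confirmation is scheduled for them.
4. Reconcile section 8.3.3 with section 8.2.3 and footnote 10, so that both arms have the same scheduled CT and response assessments. Otherwise the next scheduled scan could still be discretionary in Arm 2.

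**Cost.** Wording changes only, with no scans beyond those footnote 10 already schedules. The downside is that confirmation from cycle 7 on may come at 9 to 13 weeks instead of 4 to 8.
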